#### Clinical effectiveness measured as quality-adjusted survival over 2 years

The emphasis in cost-effectiveness studies is on estimation rather than hypothesis testing so that formal sample size calculations are less important. However, we provide a power calculation based on the effectiveness measure QALY. We could find no studies reporting comparative QALYs in similar patients undergoing ablation and cardiac surgery. From previous studies of patients undergoing angiography for suspected ischaemic heart disease[14] and patients with refractory angina[15] the standard deviation of QALYs over 12 and 18 months is at most 0.3. Over follow up of 2 years the minimum clinically important improvement is considered to be one extra month of quality-adjusted life, or 0.083 QALYs. With a sample of 200 patients per group, total 400, we would have approximately 80% power to detect a difference of 0.083 QALYs, (2-sided significance 5%). If the accepted threshold for cost effectiveness were in the range £20-30,000 per QALY and we could demonstrate a significant increase in QALYs of 0.0833, then the procedure would be cost-effective for an incremental cost of at most £2,500.

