### 2.3 Missing data

Data management will focus on the consenting process, participant eligibility, safety, data consistency and test outcomes. Attempts will be made to retrieve missing data on these areas via a thorough data cleaning process.

The levels of missing data and reasons for missingness will be investigated for the consenting process, participant eligibility, safety, data consistency and test outcomes. The quantity of missing data will be monitored by treatment group, and a summary of the number of patients with missing primary endpoint data and the quantity of missing data by treatment group will be reported.

For the intermediate primary endpoint (return to sinus rhythm at 12 months), if a patient withdraws consent or is lost to follow-up for further participation within 12 months, multiple imputation used to impute missing outcome (AF or SR at 12 months) as a function of the baseline heart rhythm, surgeon, surgical procedure and treatment group. Rubin's rules will be used to combine imputed datasets. If more than 5% of patients are withdrawn or lost to follow-up before 12 months, then the outcome will be imputed under the alternative patterns as sensitivity analyses. (See section 5.4.1)

For the final primary endpoint (Quality-Adjusted Survival at 2 years), where a patient is deceased before the end of follow-up, the utility value of 0 will be imputed for all

subsequent assessments. If the response is missing, and the patient is not known to be deceased, the missing value will be imputed using the method of multiple imputation. A “Last Observation Carried Forward” approach will be used as an alternative imputation technique for imputing other (non-death) missing values in a sensitivity analysis.

The primary analysis model will only require the baseline rhythm, surgeon and surgical procedure which are immediately recorded when patients attend the preadmission clinic and has consented to participate or during the period of surgery, so there is little concerns about missing data arising in this model. If any missing values in the covariates are reported, they will be imputed using a function of the known covariates and primary outcomes of interest.

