#### 4.5 ONS tracking

All patients enrolled in this trial (with their consent) are registered with the Office of National Statistics (ONS) Tracking System to allow long term follow up of survival. ONS tracking data is not expected to form part of the primary analysis of outcomes up to 24 months. Instead, this will be used to follow-up patients over a longer period if longer-term follow-up analyses are required.

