### 5.1 General calculations

All statistical analyses and reporting will comply with CONSORT guidelines where possible.

Confidence intervals for a single proportion shall be calculated using the Exact method. Confidence intervals for a difference between independent proportions shall be calculated using Exact intervals (Method 8 of [16]).

All percentages will be calculated using the total number of patients within the specified analysis population, percentages will be reported to 1 decimal place. All statistical tests will be 2-sided and performed at the 5% significance level. All analyses will be carried out using SAS.

For summary statistics, the number of non-missing items, the means, standard deviations, medians, upper and lower quartiles and minima and maxima will be summarised to one more decimal place than the data are collected.

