### 5.4 Analysis of Primary Endpoints

#### Quality-Adjusted Survival

For the final primary outcome, QALYs will be estimated from serial measurements of the EQ-5D for each patient up to 2 years using interpolation. The Health Economics analysis will be given in Section 6.

At baseline, on discharge and at 6 weeks, 6 months, 12 months and 24 months post-surgery all patients complete the EuroQol questionnaire, including the EQ-5D. The social tariff for the EQ-5D, as estimated by Dolan et al. [17] will be applied to each patient's self-reported classification in order to calculate utility values. Using actual rather than nominal times of assessment, and assuming a linear change in values between time points, patient-specific utility curves up to 24-months post randomisation will be calculated. A value of zero will be applied at the date of death for those patients who died.

The QALYs experienced by each patient to 24-months post randomization are calculated as the area under their utility curve to 24 months or time of death, whichever occurs first, where the true test dates rather than nominal test dates will be utilized in plotting the utility curve. In order to adjust for differences in baseline utilities a linear regression will be fitted to the utilities post treatment, with baseline utility and treatment group as explanatory variables. The linear regression will also include a random effect for surgeon if it is feasible to fit, and yields a positive variance component for the surgeon effect. Adjusted treatment effects will be taken from the treatment group coefficient of this regression. For patients who do not complete all EuroQoL measurements and are censored the methods of Willan and Lin[18] will be used to estimate mean QALYs and costs. The adequacy of model fit for the linear regression model at each timepoint will be assessed by examining distributions of standardised residuals, association with the predicted values, as well as identifying influential observations by referring to leverage statistics.

The differences in Quality-adjusted Survival will be presented. A confidence interval for the true difference will be formed using a non-parametric bootstrap resampling approach: [19]

A simple random sample with replacement will be drawn from the full analysis dataset of the same size as the full dataset. (ie some patients may be drawn more than once)

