The difference in QALYs between the two treatment groups will be estimated for this bootstrap sample.

Steps (1) and (2) will be repeated 1000 times.

The 95% confidence interval will be formed as the interval between the 2.5% and the 97.5% percentile of the differences computed in these bootstrap samples.

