#### 5.4.1 Sensitivity Analysis

For the final primary endpoint (Quality-adjusted Survival), we will impute as zero any EQ5D utility value that is missing due to the patient death. Any remaining missing values will be imputed using multiple imputation. For the sensitivity analysis, a Last Observation Carried Forward approach will be used to impute missing (nonzero) utility values at 24 months, and any missing intermediate utility values. Alternative imputation techniques will be considered. We will additionally consider a sensitivity analysis using SF6D-derived utility values and other valuation methods as appropriate.

If missing, the intermediate primary endpoint (heart rhythm) will be estimated by multiple imputation technique. If more than 5% of patients are withdrawn or lost to follow-up before the 12 months is reported, then the following methods will be used as sensitivity analyses to estimate the primary endpoint:

1. a 'death=AF, censored=AF' strategy: If a patient is withdrawn or lost to follow-up within the 12 months, he will be assumed to be in AF.

2. a 'death=AF, censored=OMIT' strategy: If a patient dies for any cause within 12 months, he will be assumed to be in AF at 12 months. If a patient is withdrawn or lost to follow-up but is alive within 12 months, his record will not be included into the sensitivity analysis.

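### For patients lost or withdrawn before 24 months, the SAP gives the QALY endpoint two missing-data methods without saying which is primary, and by default it does not use ONS deaths

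*SAP*

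**What the plan says.** - **Section 2.3.** For the final primary endpoint, utility is set to 0 at assessments after a known death. If a response is missing and the patient is not known to have died, "the missing value will be imputed using the method of multiple imputation". Last observation carried forward (LOCF) is the alternative, as a sensitivity analysis.
- **Section 5.4.1.** The rule is repeated: zero for values missing because of death, then "Any remaining missing values will be imputed using multiple imputation". LOCF is again the sensitivity analysis.
- **Section 5.4, Quality-Adjusted Survival.** "For patients who do not complete all EuroQoL measurements and are censored", the method of reference [18] is to estimate mean QALYs and costs. The reference list shows from its title that this is inverse weighting for censored data.
- **Section 4.5.** Consenting patients are registered with ONS for survival, but "ONS tracking data is not expected to form part of the primary analysis of outcomes up to 24 months".
- **Section 5.4, bootstrap steps.** Patients are resampled from the full analysis dataset, then "The difference in QALYs between the two treatment groups will be estimated for this bootstrap sample". This is done 1000 times and a percentile interval is taken. Imputation is not mentioned in these steps. Section 2.3 names Rubin's rules only for the rhythm endpoint.

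**The concern.** Imputation and inverse weighting are different estimators. Imputation fills in the missing utilities from a model and keeps every patient. Weighting leaves the censored time unfilled and lets observed patients stand for it. If all non-death gaps are imputed, as sections 2.3 and 5.4.1 require, nobody is left to weight. If the section 5.4 sentence is followed, patients lost to follow-up are not imputed. Two statisticians working faithfully from this SAP could therefore report different primary QALY results, and the choice could be made after the data are seen.

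The ONS default acts on the same patients. The zero-utility rule works only for deaths the trial knows about. A patient who drops out and then dies, with the death visible only to ONS, counts as not known to be deceased. Imputation gives that patient a living utility, LOCF carries one forward, and weighting treats the patient as censored alive. None of the planned analyses would reveal the error.

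Finally, if imputation were done once and the completed data then bootstrapped, the percentile interval would not carry the uncertainty of the imputed values.

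**Working it through.** **1. Design figure, for scale.** Inputs from section 1.4.1: "the minimum clinically important improvement is considered to be one extra month of quality-adjusted life, or 0.083 QALYs", SD at most 0.3, 200 per group. From section 5.1: "All statistical tests will be 2-sided and performed at the 5% significance level". The standard error of the difference is 0.3 × √(2/200) = 0.030. Power = Φ(0.083/0.030 − 1.96) = Φ(0.807) = 79.0%. The plan states "With a sample of 200 patients per group, total 400, we would have approximately 80% power to detect a difference of 0.083 QALYs", so its figure is reproduced. The yardstick below is 0.083.

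**2. The rules side by side, by type of patient.**

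| Patient | Sections 2.3 and 5.4.1 | Section 5.4 |
|---|---|---|
| Known to have died | zero after death | zero at date of death |
| Still followed, an assessment missed | multiple imputation | not covered (not censored) |
| Lost or withdrawn before 24 months | multiple imputation | inverse weighting, reference [18] |
| Lost, death seen only by ONS | multiple imputation (not known dead) | inverse weighting, as censored |

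Only the last two rows conflict.

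**3. Can the two methods differ?** This was illustrated on assumed data: 200 per arm, about 11.5% of 24-month values missing, and missingness depending on the 12-month utility more strongly in one arm. Regression imputation stood in for multiple imputation, and weighting used a marginal censoring probability in each arm. Mean treatment differences over 2000 simulated trials were:

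- full data: 0.058
- imputation: 0.058
- inverse weighting: 0.066

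The gap is about 0.008, and 0.008/0.083 is about 10%. The size depends wholly on these assumptions. The exercise shows only that the two rules need not agree on the same data.

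**4. A death seen only by ONS.** Over-credit to the arm mean = utility × years from death to month 24 ÷ 200. The SAP gives neither utility nor timing, so utility 0.75 and 1 to 1.5 years are assumed.

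- 0.75 × 1 / 200 = 0.0037; 0.75 × 1.5 / 200 = 0.0056. Each missed death is worth 4.5% to 6.8% of 0.083.
- Wider assumptions (utility 0.6-0.8, 0.5-1.5 years) give 0.30-1.20 QALYs per patient, or 0.0015-0.006 on the arm mean.
- Excess of such deaths in one arm needed to produce 0.083 alone: 200 × 0.083 / 1.20 = 14, up to 200 × 0.083 / 0.30 = 55.

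**5. Bootstrap after a single imputation.** Ratio of true to reported standard error = √[1 + m/(1 − m) × (1 − R²)], where m is the fraction of patients with missing data and R² is the share of QALY variance explained by what is observed. Coverage = 2Φ(1.96/ratio) − 1. The SAP gives neither input; m = 0.15-0.25 is assumed throughout.

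- With R² of 0.2-0.4: m = 0.15, R² = 0.4 gives ratio 1.05 and coverage 94%; m = 0.25, R² = 0.2 gives 1.13 and 92%.
- The QALY is an area over six assessments, so a patient lost late still contributes most of it. Assuming equal correlation of 0.3-0.7 between assessments and nominal visit times, R² is 0.90-0.97 if only month 24 is missing and 0.62-0.89 if months 12 and 24 are missing.
- Over R² of 0.62-0.97 the ratio is 1.00-1.06 and coverage about 93.5-95%.
- Only with months 6, 12 and 24 all missing and correlation 0.3 does R² fall to 0.44; coverage is then about 93-94%.

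**The case against.** The strongest defence is that the methods divide the work: imputation for gaps, weighting for censoring. That would be coherent, but the SAP does not say so, and sections 2.3 and 5.4.1 cover all non-death missing values. A second defence is that the sentence on reference [18] belongs to the health-economic analysis, since it also mentions costs. That is possible. However, it stands inside the primary QALY analysis, and the SAP leaves health economics to a separate plan, so as written it governs this endpoint. It is fair to say that imputation has the better claim to be the intended base case, because two sections assign it to this endpoint by name.

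Three stronger readings are tempting and are not supported:

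- **That ONS deaths are barred.** Section 4.5 states an expectation, not a prohibition. Section 4.3 collects mortality after surgery, with contacts at discharge, 6 weeks, 6, 12 and 24 months and yearly by telephone thereafter. Only deaths that escape this matter, and the SAP gives no basis for counting them.
- **That the treatment effect is inflated.** A missed death always raises its own arm's mean. The difference moves only if such deaths are unbalanced, and it can move either way. A scenario with five missed deaths in one arm and none in the other (0.019-0.028 QALYs) is arithmetically right but has no support in the document.
- **That the interval is too narrow.** The bootstrap steps do not say that imputation is done once beforehand. Imputing again within each sample is compatible with the text. The fair criticism is that the order is not stated.

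**Conclusion.** The contradiction stands for patients lost or withdrawn before 24 months. For them the final primary endpoint has two assigned methods and no ranking. Its numerical effect cannot be fixed from the SAP; 0.008 QALYs (10% of the target) is an illustration under assumed missingness. What does not depend on those assumptions is that the choice is left open.

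The ONS point holds in a smaller form: about 0.004-0.006 QALYs on an arm mean per missed death, given utility 0.75 and 1-1.5 years credited, with an unknown number of such deaths and no predictable direction for the treatment difference. The bootstrap point is a gap in specification, and any loss of coverage is probably small. Severity is SHOULD-FIX. A reader might infer that the whole QALY result is unreliable or biased in favour of one arm; the document does not support that.

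**What to change.** 1. In section 5.4, name multiple imputation as the single primary method for all utilities missing for reasons other than death, in line with sections 2.3 and 5.4.1. List the inverse-weighted estimate among the sensitivity analyses in section 5.4.1.
2. In section 4.5, replace the default of not using ONS data with a check of ONS death dates to 24 months for all consenting patients, made before imputation. Apply zero utility from that date.
3. In the bootstrap steps of section 5.4, state that imputation is repeated within each bootstrap sample, so that the percentile interval carries imputation uncertainty.

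The cost is SAP wording, one status check at data lock on registrations already in place, and longer computing time.

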### 5.2 General principles

Multivariable analyses will not be 'built' following a model-fitting strategy. Instead, all variables specified for inclusion will be added to the model, and the significance of each factor will be reported. Where one categorical variable has more than one 'factor level' then the significance of overall effect of including all factor levels will be tested, rather than those for each individual factor level. For all factor levels, suitable point and interval estimates of effect size will be presented.

If any analysis requires the use of simulation and / or re-sampling methods, the initial 'seed' value for the random number generation will be 0471346543. The same seed will be used at the start of every such analysis.

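### The 95% limits for the QALY difference come from only 1000 bootstrap samples, which leaves a small, avoidable simulation error in the interval for the final primary endpoint

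*SAP*

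**What the plan says.** For the final primary endpoint, SAP section 5.4 (Quality-Adjusted Survival) states: "A confidence interval for the true difference will be formed using a non-parametric bootstrap resampling approach". Patients are resampled with replacement and the QALY difference is re-estimated in each sample. On the number of samples it says: "Steps (1) and (2) will be repeated 1000 times". The 95% interval is then "formed as the interval between the 2.5% and the 97.5% percentile of the differences computed in these bootstrap samples". Section 5.4 names no other interval for the QALY difference.

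Section 5.2 fixes one seed for all resampling and adds: "The same seed will be used at the start of every such analysis". It also has a general rule that the significance of each factor in a multivariable model is reported. Section 5.1 sets the testing standard: "All statistical tests will be 2-sided and performed at the 5% significance level".

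The SAP gives no target for the simulation error of the limits and no rule for adding samples when a limit lands near zero.

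**The concern.** A percentile limit is an estimated tail quantile. With 1000 samples it rests on the 25 or so most extreme values on each side, so rerunning the bootstrap on the same patients with another seed would move it. Fixing the seed settles in advance which run is reported and prevents anyone choosing a favourable one. It does not bring that run closer to the answer that unlimited resampling would give.

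What is at stake is limited. The reported limits are slightly less precise than the data allow. If a limit happens to lie very close to zero, which side it falls on could be settled by simulation noise. The section 5.4 regression, if its treatment term is reported with a p-value under section 5.2, could then point the other way, and the SAP does not say how the two relate.

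**Working it through.** **Inputs, all from the SAP**
- SD of QALYs, section 1.4.1: "the standard deviation of QALYs over 12 and 18 months is at most 0.3".
- Target difference, section 1.4.1: "one extra month of quality-adjusted life, or 0.083 QALYs".
- Sample size, section 1.4.1: "With a sample of 200 patients per group, total 400".
- Two-sided 5% level, section 5.1.
- B = 1000 bootstrap samples with 2.5% and 97.5% percentiles, section 5.4.

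The calculation assumes complete data, an unadjusted difference in means and a roughly normal bootstrap distribution.

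**Step 1: reproduce the plan's power.** SE = 0.3 × √(2/200) = 0.030 QALY. Power = Φ(0.083/0.030 − 1.96) = Φ(0.807) = 79.0%, in line with the stated figure of about 80%. The expected 95% interval is 2 × 1.96 × 0.030 = 0.118 QALY wide.

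**Step 2: simulation error of a limit.** In units of the SE it is s = √(0.025 × 0.975/B)/φ(1.96), with φ(1.96) = 0.0584.
- B = 1000: s = 0.00494/0.0584 = 0.0845. Times 0.030, this is 0.0025 QALY, about 3% of the 0.083 target. The 95% simulation range is ±1.96 × 0.0025 = ±0.005 QALY.
- B = 10,000: s = 0.0267, or 0.0008 QALY.

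If the SD were 0.2 to 0.5 (an assumed range, since the quoted SD refers to 12 and 18 months and not to two years), the figure at B = 1000 would be about 0.0017 to 0.0042 QALY.

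**Step 3: the zone in which noise matters.** With B = 1000 the tail area actually cut off ranges over 0.025 ± 1.96 × 0.00494, that is 1.5% to 3.5%. Doubled, this is a two-sided p between about 0.031 and 0.069. With B = 10,000 the zone is about 0.044 to 0.056.

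**Step 4: how often the reading of zero would change.** For an estimate z standard errors from zero, the number of bootstrap differences on the far side of zero is binomial with probability Φ(−z). I compared that count with 2.5% of B and averaged over z ~ N(μ, 1). This gives the chance that the interval disagrees with one from unlimited samples:

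| True effect | B = 1000 | B = 10,000 |
|---|---|---|
| none (μ = 0) | 0.8% | 0.2% |
| at the significance boundary (μ = 1.96) | 2.7% | 0.9% |
| design effect (μ = 0.083/0.030 = 2.77) | 1.9% | 0.6% |

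A hand check for the last row is 2sφ(0)φ(1.96 − μ) = 2 × 0.0845 × 0.399 × 0.288 = 0.019 at B = 1000, and 0.006 with s = 0.0267.

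**Step 5: average error rates.** Read as a test, the interval has type I error of 5.1% with B = 1000 against 5.0% with unlimited samples. Power is 79.0% in both cases.

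**Step 6: check by simulation.** One dataset of 200 per group was constructed so that its lower limit lay almost exactly at zero, then bootstrapped repeatedly. With B = 1000 (400 repeats) the lower limit had an SD of 0.0025 QALY, as in step 2, and zero was excluded in 55% of repeats with the patients unchanged. With B = 10,000 (60 repeats) the SDs of the two limits were 0.0006 and 0.0009. A dataset placed on the boundary will divide its repeats at any B. What the larger B does is narrow the band of datasets for which this happens.

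**The case against.** The strongest case against raising this is that nothing important changes. Added in quadrature, the simulation error raises the variability of a limit by a factor of √(1 + 0.0845²) = 1.0036, or about 0.4%. Type I error and power barely move. An error of 0.0025 QALY is about 0.9 of a day in full health (0.0025 × 365), against a target of one month. The SAP fixes the method, the number of samples, the percentiles and the seed, and no tolerance in the document is breached by 1000. All of this stands, and it is why the point is minor.

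A reader might also infer that section 5.4 specifies no QALY test, so that the trial's verdict hangs on these limits alone. The SAP does not support that. The treatment effect is the coefficient of a linear regression, and the general rule in section 5.2 can be read as requiring its significance to be reported, independently of the bootstrap draw. No rule makes exclusion of zero by the bootstrap interval the criterion, and section 1.4.1 puts estimation ahead of testing for this endpoint. What remains is narrower: this is the one interval section 5.4 names for the QALY difference, and near zero its noise could set it at odds with such a p-value.

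Finally, more samples are not free. Sections 2.3 and 5.4.1 call for multiple imputation and section 5.4 for a surgeon random effect where feasible. The SAP does not say whether these are redone within each sample. That objection also stands and belongs in the cost.

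**Conclusion.** The point holds as a small, avoidable imprecision in the interval for the final primary endpoint. Each limit carries a simulation standard error of about 0.0025 QALY with 1000 samples, and the fixed seed does not reduce it. Noise can settle the side of zero only when a limit lies within about 0.005 QALY of it. Under the design effect the reading would differ from that of unlimited resampling in about 1.9% of trials.

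It would be wrong to infer that the interval is invalid, that error rates are compromised, or that the result generally depends on the draw and not on the patients. The figures in steps 4 and 5 rule that out.

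The sizes rest on the plan's SD of 0.3, 200 analysed per group, complete data and an unadjusted difference. Baseline adjustment, imputation or a different SD would change the QALY figures in proportion to the sampling SE. The ratio of 0.0845 depends on B and on the approximately normal shape of the bootstrap distribution.

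**What to change.** In the bootstrap steps of SAP section 5.4, change the number of repetitions from 1000 to 10,000 and keep the seed stated in section 5.2. The simulation standard error of each limit falls by a factor of √10, about 3.2, to about 0.0008 QALY. Discordance at the design effect falls to about 0.6%. The estimand, the regression and the type of interval stay as they are.

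The cost is one number in the SAP and roughly ten times the computing time. That is more noticeable if multiple imputation or the surgeon random effect is refitted in every sample.
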